### 10.1.1 Exposure during the Initial Treatment Period for SS

Definitions for study medication duration (days) and time at risk (days) during the Initial Treatment Period are provided as follows:

#### Study medication duration (days)

- Date of last active dose of IMP in the Initial Treatment Period – date of first dose + 28 days  
Note: If date of last active dose of IMP in the Initial Treatment Period + 28 days extends to a date beyond the final visit date (including PEOT, but not including SFU), then this calculation reverts to:
  - Final visit date (including PEOT, but not including SFU) – date of first dose + 1.  
Note: If date of last active dose of IMP in the Initial Period + 28 days extends to a date beyond the date of first dose in the Maintenance Treatment Period, then this calculation reverts to:
    - Date of first dose in the Maintenance Period – date of first dose in the Initial Treatment Period + 1.

Note: For subjects who die, if date of last active dose of IMP in the Initial Treatment Period + 28 days extends to a date beyond the date of death, then this calculation reverts to:

- Date of death – date of first dose + 1.

Time at risk (days)

- For subjects who die:
  - Date of death – date of first dose + 1.
- For subjects who complete the final visit of the Initial Period and continue to the Maintenance Period:
  - Date of first dose in the Maintenance Treatment Period – date of first dose in the Initial Treatment Period + 1.
- For subjects who discontinue on or prior to the final visit of the Initial Period, use the minimum of the following:
  - Date of last active dose of IMP in the Initial Treatment Period – date of first dose + 140 days.
  - The total number of days in the Initial Treatment Period (112 days). For AEs that emerged after 112 days but still within the 140 days window, those AEs would be classified as TEAE, but will be excluded from the output based on the Initial Treatment Period. However, these AEs will be included in the AE summaries for Initial Treatment Period and Maintenance Treatment Period combined.
  - Date of last clinical contact – date of first dose + 1.

### 10.1.2 Exposure during the Maintenance Treatment Period for MS

Definitions for study medication duration (days) and time at risk (days) during the Maintenance Treatment Period are provided as follows:

Study medication duration (days)

- Date of last bimekizumab or secukinumab dose in the Maintenance Treatment Period – date of first dose in the Maintenance Treatment Period + 28 days (for subjects on Q4W dosing or secukinumab)
- Date of last bimekizumab in the Maintenance Treatment Period – date of first dose in the Maintenance Treatment Period + 56 days (for subjects on Q8W dosing)

Note: If date of last bimekizumab or secukinumab dose in the Maintenance Treatment Period + 28 days (or 56 days for subjects on Q8W dosing) extends to a date beyond the final visit date (including PEOT, but not including SFU), then this calculation reverts to:

- Final visit date (including PEOT, but not including SFU) – date of first dose in the Maintenance Treatment Period + 1.

Note: If date of last bimekizumab or secukinumab dose in the Maintenance Period + 28 (or 56 days for subjects on Q8W dosing) days extends to a date beyond the date of first dose in the Open-Label Extension Period, then this calculation reverts to:

- Date of first dose in the Open-Label Extension Period – date of first dose in the Maintenance Treatment Period + 1.

Note: For subjects who die, if date of last bimekizumab or secukinumab dose in the Maintenance Treatment Period + 28 days (or 56 days for subjects on Q8W dosing) extends to a date beyond the date of death, then this calculation reverts to:

- Date of death – date of first dose in the Maintenance Treatment Period + 1.

Time at risk (days)

- For subjects who die:
  - Date of death – date of first dose in the Maintenance Treatment Period + 1.
- For subjects who complete the final visit of the Maintenance Period and continue to the OLE Period:
  - Date of first dose in the OLE Period - date of first dose in the Maintenance Treatment Period + 1 day.
- For subjects who discontinue on or prior to the final visit of the Maintenance Period, use the minimum of the following:
  - Date of last dose in the Maintenance Treatment Period – date of first dose in the Maintenance Treatment Period + 140 days.
  - Date of last clinical contact – date of first dose in the Maintenance Treatment Period + 1.

### 10.1.3 Exposure during the Initial and Maintenance Treatment Period for SS

Definitions for study medication duration (days) and time at risk (days) during the Initial and Maintenance Treatment Period are provided as follows:

#### 10.1.3.1 For subjects who do not switch study treatments

Study medication duration (days)

- Date of last active dose of IMP in the Initial and Maintenance Treatment Period – date of first dose + 28 days

Note: If date of last active dose of IMP in the Initial and Maintenance Treatment Period + 28 days extends to a date beyond the final visit date (including PEOT, but not including SFU), then this calculation reverts to:

- Final visit date (including PEOT, but not including SFU) – date of first dose + 1.

Note: If date of last bimekizumab or secukinumab dose in the Maintenance Period + 28 days extends to a date beyond the date of first dose in the Open-Label Extension Period, then this calculation reverts to:

- Date of first dose in the Open-Label Extension Period – date of first dose + 1.

Note: For subjects who die, if date of last dose in the Initial Treatment and Maintenance Period + 28 days extends to a date beyond the date of death, then this calculation reverts to:

- Date of death – date of first dose + 1.

Time at risk (days)

- For subjects who continue into the OLE period:

- Date of first dose in the OLE Period – date of first dose + 1.
- For subjects who die: Date of death – date of first dose +1.
- For all other subjects, use the minimum of the following:
  - Date of last active dose of IMP in the Initial and Maintenance Treatment Period– date of first dose + 140 days.
  - Date of last clinical contact – date of first dose + 1.

### 10.1.3.2 For subjects who switch from BKZ 320mg Q4W to Q8W at Week 16:

Study medication duration (days)

- Initial Treatment Period (attributed to BKZ 320mg Q4W)
  - Date of last dose in the Initial Treatment Period – date of first dose + 28 days

Note: If date of last dose in the Initial Treatment Period + 28 days extends to a date beyond the first dose in the Maintenance Treatment Period, then this calculation reverts to:

  - Date of first dose in the Maintenance Treatment Period – date of first dose + 1.
- Maintenance Treatment Period (attributed to BKZ 320mg Q8W)
  - Use the study medication duration algorithm specified for the Maintenance Treatment Period in Section 10.1.2
- Initial and Maintenance Treatment Period (attributed to Total BKZ)
  - Study medication duration in Initial Treatment Period + Study medication duration in Maintenance Treatment Period.

Time at risk (days)

- Initial Treatment Period (attributed to BKZ 320mg Q4W)
  - Date of first dose in the Maintenance Treatment Period - date of first dose + 1 day.
- Maintenance Treatment Period (attributed to BKZ 320mg Q8W)
  - Use the time at risk algorithm specified for the Maintenance Treatment Period in Section 10.1.2
- Initial and Maintenance Treatment Period (attributed to Total BKZ)
  - Use the time at risk algorithm specified for subjects who do not switch study treatments in Section 10.1.3.1

### 10.1.4 Exposure during the Open-Label Extension Period based on OLS

Definitions for study medication duration (days) and time at risk (days) during the Open-Label Extension Period are provided as follows:

#### 10.1.4.1 For subjects who do not switch study treatments

Study medication duration (days)

- For subjects who receive Q4W in the Open-Label Extension Period (subjects who discontinue prior to switching to Q8W):
  - Date of last bimekizumab dose in the Open-Label Extension Period – date of first dose in the Open-Label Extension Period + 28 days (for subjects on Q4W dosing)
- For subjects who receive Q8W in the Open-Label Extension Period use the minimum of:
  - Date of last bimekizumab dose in the Open-Label Extension Period – date of first dose in the Open-Label Extension Period + 56 days
  - First dose date in Open-Label Extension 2 Period – date of first dose in the Open-Label Extension Period + 1

Note: If date of last bimekizumab dose in the Open-Label Extension Period + 28 days (or 56 days for subjects on Q8W dosing) extends to a date beyond the final visit date (including PEOT, but not including SFU), then this calculation reverts to:

- Final visit date (including PEOT, but not including SFU) – date of first dose in the Open-Label Extension Period + 1.

Note: For subjects who die, if date of last bimekizumab dose in the Open-Label Extension Period + 28 days (or 56 days for subjects on Q8W dosing) extends to a date beyond the date of death, then this calculation reverts to:

- Date of death – date of first dose in the Open-Label Extension Period + 1.

Time at risk (days)

- For all subjects, use the minimum of the following:
  - Date of last dose in the Open-Label Extension Period – date of first dose in the Open-Label Extension Period + 140 days,
  - Date of first dose in OLE2 - date of first dose in the Open-Label Extension Period + 1 day
  - Date of last clinical contact in OLE and SFU – date of first dose in the Open-Label Extension Period + 1.
  - Date of death – date of OLE first dose

#### 10.1.4.2 For subjects who switch from BKZ 320mg Q4W to Q8W during Open-Label Extension Period

Following Protocol Amendment 5.0, subjects receiving Q4W should switch to Q8W during the Open-Label extension period. (see Section 2.3.2.4 for further details).

Study medication duration (days)

- Attributed to BKZ 320mg Q4W:
  - Date of last BKZ 320mg Q4W dose in the OLE Period – date of first BKZ 320mg Q4W dose in the OLE Period + 28 days

Note: If date of last BKZ 320mg Q4W dose in the OLE Period + 28 days extends to a date beyond the date of first BKZ 320mg Q8W dose in the OLE Period, then this calculation reverts to:

- Date of first BKZ 320mg Q8W dose in the OLE Period – date of first BKZ 320mg Q4W dose in the OLE Period + 1.
- Attributed to BKZ 320mg Q8W use the minimum of:
  - Date of last BKZ 320mg Q8W dose in the OLE Period – date of first BKZ 320mg Q8W dose in the OLE Period + 56 days.
  - First dose date in Open-Label Extension Period 2 – date of first BKZ 320mg Q8W dose in the Open-Label Extension Period + 1.

Note: If date of last bimekizumab dose in the Open-Label Extension Period + 56 days extends to a date beyond the final visit date (including PEOT, but not including SFU), then this calculation reverts to:

- Final visit date (including PEOT, but not including SFU) – date of first BKZ 320mg Q8W dose in the OLE Period + 1.

Note: For subjects who die, if date of last bimekizumab dose in the Open-Label Extension Period + 56 days extends to a date beyond the date of death, then this calculation reverts to:

- Date of death – date of first BKZ 320mg Q8W dose in the OLE Period + 1.
- Attributed to Total BKZ
  - Sum of study medication duration in OLE period attributed to BKZ 320mg Q4W and study medication duration in OLE period attributed to BKZ 320mg Q8W-1.

Time at risk (days)

- Attributed to BKZ 320mg Q4W:
  - Date of first BKZ 320mg Q8W dose in the OLE Period – date of last BKZ 320mg Q4W dose in the OLE Period + 1 day
- Attributed to BKZ 320mg Q8W:
  - For all subjects, use the minimum of the following:
    - Date of last BKZ 320mg Q8W dose in the OLE Period – date of first BKZ 320mg Q8W dose in the OLE Period + 140 days.
    - Date of first BKZ 320mg Q8W dose in OLE2 - date of first BKZ 320mg Q8W dose in the Open-Label Extension Period + 1 day
    - Date of last clinical contact – date of first BKZ 320mg Q8W dose in the OLE Period + 1.
    - Date of death – date of first BKZ 320mg Q8W dose in the OLE Period + 1.
- Attributed to Total BKZ:

- Use the time at risk algorithm specified for subjects who do not switch study treatments in Section [10.1.4.1](#)

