**Table 7-2: Dosing scheme, OLE Period**

Week	48 (1st OLE dose)	Year 2											Year 3													
		52	56	60	64 ab	68	72 ab	76	80	84 ac	88	92	96 ab	100	104	108 ac	112	116	120 ab	124	128	132 ac	136	140		
Bimekizumab 320mg Q4W	●●	●●	●●	●●	●●	●●	●●	●●	●●	●●	●●	●●	●●	●●	●●	●●	●●	●●	●●	●●	●●	●●	●●	●●	●●	●●
Bimekizumab 320mg Q8W	●●		●●		●●		●●		●●		●●		●●		●●		●●		●●		●●		●●		●●	

OLE=Open-Label Extension; Q4W=every 4 weeks; Q8W=every 8 weeks

Notes: A bimekizumab 160mg injection is depicted by a black circle (●).

a The subject's dosing interval will change from Q4W to Q8W at Week 64 or at the next scheduled clinic visit after implementation of Protocol Amendment 5.0 if the subject has already completed the Week 64 visit.

b Subjects whose dosing interval is changed to Q8W should be dosed at this visit and will receive kits for home administration 8 weeks later.

c Subjects whose dosing interval is changed to Q8W should NOT be dosed at this visit and will receive kits for home administration 4 weeks later.

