#### 10.1.6.2.2 Subjects reinitiated to receive BKZ Q4W/Q8W at OLE2 start

- Attributed to BKZ Q4W/Q8W

- Date of last BKZ 320mg Q8W dose in the OLE2 Period – date of first BKZ 320mg Q4W dose in the OLE2 Period + 56 days.

Note: If date of last bimekizumab dose in the OLE2 Period + 56 days extends to a date beyond the final visit date (including PEOT, but not including SFU2), then this calculation reverts to:

- Final visit date (including PEOT, but not including SFU2) – date of first BKZ 320mg Q4W dose in the OLE2 Period + 1.

Note: For subjects who die, if date of last bimekizumab dose in the OLE2 Period + 56 days extends to a date beyond the date of death, then this calculation reverts to:

- Date of death – date of first dose in the OLE2 Period + 1

- If the subject discontinued prior to the switch to Q8W then:

- Date of last BKZ 320mg Q4W dose in the OLE2 Period – date of first BKZ 320mg Q4W dose in the OLE2 Period + 28 days.

If date of last bimekizumab dose in the OLE2 Period + 28 days extends to a date beyond the final visit date (including PEOT, but not including SFU2), then this calculation reverts to:

- Final visit date (including PEOT, but not including SFU2) – date of first BKZ 320mg Q4W dose in the OLE2 Period + 1.

Note: For subjects who die prior to switch to Q8W, if date of last bimekizumab dose in the OLE2 Period + 28 days extends to a date beyond the date of death, then this calculation reverts to:

- Date of death – date of first dose in the OLE2 Period + 1.

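### The 28-day credit for the last Q4W dose drops 28 planned treatment days from the OLE medication duration of subjects switched to Q8W at the undosed visits (Weeks 84, 108, 132)

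*SAP*

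**What the plan says.** Section 10.1.4.2 of the SAP builds study medication duration for OLE switchers from two parts.

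- **Q4W part:** the date of the last Q4W dose minus the "date of first BKZ 320mg Q4W dose in the OLE Period + 28 days". The one adjustment applies when this credit "extends to a date beyond the date of first BKZ 320mg Q8W dose in the OLE Period", in which case the part is cut back. Nothing lengthens it when the first Q8W dose comes later.
- **Q8W part:** the date of the last Q8W dose minus the "date of first BKZ 320mg Q8W dose in the OLE Period + 56 days", with caps at the first OLE2 dose, the final visit and death.
- **Total BKZ:** "Sum of study medication duration in OLE period attributed to BKZ 320mg Q4W" plus the Q8W part, less 1.

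Table 7-2 sets the timing of the switch. Footnote a says the interval "will change from Q4W to Q8W at Week 64 or at the next scheduled clinic visit" once Protocol Amendment 5.0 is in force. The columns so marked are Weeks 64, 72, 84, 96, 108, 120 and 132. At Weeks 64, 72, 96 and 120 (footnote b) the subject is dosed at the switch visit. At Weeks 84, 108 and 132 footnote c applies: "Subjects whose dosing interval is changed to Q8W should NOT be dosed at this visit and will receive kits for home administration 4 weeks later".

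Section 10.1.5.2 uses the same 28-day credit for the last consecutive Q4W dose when durations are summed over periods for the BKZ Set. Section 10.1.6.2.2 handles the Q4W/Q8W group in OLE2 differently, as one span: "Date of last BKZ 320mg Q8W dose in the OLE2 Period – date of first BKZ 320mg Q4W dose in the OLE2 Period", plus 56 days.

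**The concern.** A 28-day credit suits a Q4W dose when the next dose is due 28 days later. At a footnote-c switch the next dose is due 56 days later by design, so the credit ends halfway through a planned interval and the Q8W clock has not yet started. The subject is fully on schedule, yet 28 days are recorded as no study medication under Q4W and under Total BKZ.

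The SAP counts an interval of this length elsewhere. A subject on Q8W throughout the OLE is also dosed at Weeks 80 and 88, and Section 10.1.4.1 counts every day between. In OLE2 the move from Q4W to Q8W leaves 8 weeks between the Week 16 and Week 24 doses, and Section 10.1.6.2.2 counts them all. For the BKZ Set, the Q4W time at risk in Section 10.1.5.2 runs up to the first Q8W dose.

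At stake are the exposure summaries in days and patient-years and the cumulative duration table. Duration would differ between equally treated subjects according to which clinic visit carried the switch. The group is expected to exist: Section 9 defines PK sequences with a switch at Week 72 or 84 and at Week 96 or later.

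**Working it through.** **Inputs.** OLE first dose at Week 48, last Q8W dose at Week 136, last Q4W dose at Week 140, OLE length 96 weeks (Sections 2.3.2 and 2.3.3); switch visits and footnotes from Table 7-2; duration formulas from Sections 10.1.4.1, 10.1.4.2, 10.1.5.2 and 10.1.6.2.2. All doses are taken as exactly on schedule, and the dose before the switch visit counts as Q4W.

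**Step 1: reproduce the stated OLE length.** Without a switch:
- Q8W: (136 − 48) × 7 + 56 = 672 days
- Q4W: (140 − 48) × 7 + 28 = 672 days

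Both equal 96 × 7 = 672.

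**Step 2: apply Section 10.1.4.2 to each switch visit.** The last Q4W dose is 4 weeks before the switch visit. The first Q8W dose is at the visit (footnote b) or 4 weeks after it (footnote c).
- Q4W part = (last Q4W week − 48) × 7 + 28
- Q8W part = (136 − first Q8W week) × 7 + 56
- Total = Q4W part + Q8W part − 1

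| Switch visit | Last Q4W | First Q8W | Planned gap (days) | Q4W part | Q8W part | Total |
|---|---|---|---|---|---|---|
| 64 (b) | 60 | 64 | 28 | 112 | 560 | 671 |
| 72 (b) | 68 | 72 | 28 | 168 | 504 | 671 |
| 84 (c) | 80 | 88 | 56 | 252 | 392 | **643** |
| 96 (b) | 92 | 96 | 28 | 336 | 336 | 671 |
| 108 (c) | 104 | 112 | 56 | 420 | 224 | **643** |
| 120 (b) | 116 | 120 | 28 | 504 | 168 | 671 |
| 132 (c) | 128 | 136 | 56 | 588 | 56 | **643** |

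No cap applies on schedule: the Q4W credit never passes the first Q8W dose, and Week 136 + 56 days is exactly Week 144.

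**Step 3: size.** 671 − 643 = 28 days, and 28 / 672 = 4.2% of the OLE. Against a non-switcher the shortfall is 29 days. The extra day comes from the deduction of 1, which is made although the two parts do not overlap.

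**Step 4: Week 0 to 144 under Section 10.1.5.2, Q4W from Baseline to the switch.** The Initial part is 12 × 7 + 28 = 112 and the Maintenance part (44 − 16) × 7 + 28 = 224.
- Week 72 switch: 112 + 224 + 168 + 504 = 1008 before the n−1 deduction
- Week 84 switch: 112 + 224 + 252 + 392 = 980

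The difference is again 28 days, and 28 / 1008 = 2.8%.

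**Step 5: the OLE2 rule.** One span gives 40 × 7 + 56 = 336 days = 48 weeks. The split rule of Section 10.1.4.2 would give (16 × 7 + 28) + ((40 − 24) × 7 + 56) = 140 + 168 = 308 before any deduction, again 28 fewer.

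**The case against.** **A uniform convention.** Crediting every Q4W dose with 28 days is the SAP's general rule, and the OLE has to split time by regimen. OLE2 reports the Q4W/Q8W group in one combined column, so its single span is not an exact precedent. That is fair as far as the split goes. It does not explain why the 28 days are also absent from Total BKZ, which needs no split.

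**The row for at least 144 weeks.** A reader might infer that this rule alone keeps the affected subjects out of that row. The documents do not support this. The row needs 144 × 7 = 1008 days. Section 10.1.5.2 deducts n−1 when periods are summed, so an on-schedule Week 72 switcher, who has no gap, ends at 1006 or 1005 days depending on whether n is counted as 3 or 4, and misses the row too. Subjects randomized to secukinumab start bimekizumab at Week 48 and have at most 96 scheduled weeks by Week 144. For a Week 0 completer, 980 days is 140 weeks, so the rows for 72, 96 and 120 weeks do not move.

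**Adverse event rates.** A reader might also infer that exposure-adjusted rates are biased. Section 10.2.1 bases them on time at risk, and Total BKZ time at risk for OLE switchers uses the continuous algorithm of Section 10.1.4.1. This gap does not enter them.

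**How many subjects.** Three of the seven switch visits carry footnote c, but that is a count of visits. The SAP gives no distribution of switch times, so it says nothing about the share of subjects.

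**An over-broad remedy.** Crediting up to 56 days after any last Q4W dose would reward a late or missed dose at Week 64, 72, 96 or 120, where no 56-day interval is planned. That objection stands and limits the fix.

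**Conclusion.** The point holds in a limited form. For switches at Weeks 84, 108 and 132, the duration rule in Section 10.1.4.2, repeated in Section 10.1.5.2, does not match the SAP's own dosing table. It leaves 28 planned treatment days out of both the Q4W and the Total BKZ study medication duration: 643 days against 671 for an on-schedule completer.

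The error is confined to descriptive duration tables and touches no efficacy test or exposure-adjusted rate. The total understatement in patient-years cannot be computed, because the number of subjects affected is not stated. The figures assume on-schedule dosing and completion to Week 144. The rule should still be corrected: it gives a wrong exposure figure for fully treated subjects, and the correction is small.

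**What to change.** In Sections 10.1.4.2 and 10.1.5.2, add a sentence for switches at Table 7-2 footnote-c visits only: the Q4W duration runs from the first Q4W dose to the first Q8W dose, limited to 56 days after the last Q4W dose. Leave the 28-day rule in place for all other switch visits.

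Compute Total BKZ so that the parts join without a gap, and deduct 1 only where two parts really share a day, as when the existing cap with its +1 applies. This agrees with the continuous span in Section 10.1.6.2.2.

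On schedule, the Q4W part becomes 280, 448 or 616 days for switches at Weeks 84, 108 or 132, and the Total becomes 672 days for every OLE switcher. If the blanket deduction of 1 were kept, the Total would be 671, so the text should say which is meant.

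The cost is a short SAP edit and a rerun of the exposure tables. The change reconciles the duration rule with Table 7-2 and implies no change to dosing.

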### **2.3.2 Study periods**

This study will include 5 periods, a Screening Period (2 to 5 weeks), a double-blind Treatment Period (48 weeks; final dose at Week 44), an optional open-label extension (OLE) Period (96 weeks, final dose at Week 136 for subjects receiving bimekizumab 320mg Q8W and at Week 140 for subjects receiving bimekizumab 320mg Q4W, followed by a safety follow-up (SFU) Period (20 weeks after the final dose of IMP). Eligible subjects from US and Canada sites who have completed the OLE Period (at Week 144), including subjects in the SFU period and subjects who have completed the SFU Period will have the option to enroll in the 48-week Open-Label Extension 2 (OLE2) Period followed by a SFU Period (SFU2, 20 weeks after the final dose of IMP administered in the OLE2).

The double-blind treatment Period will be separated into an Initial Treatment Period (16 weeks) and a Maintenance Treatment Period (32 weeks). The end of the study is defined as the date of the last visit of the last subject in the study.

Subjects withdrawing early from the study will undergo the premature end of treatment (PEOT) Visit assessments and will enter the SFU Period. Following completion or early withdrawal from the OLE2 Period, subjects will undergo the SFU of the OLE2 Period (SFU2) and will return for the SFU2 Visit 20 weeks after the last dose of IMP administration in the OLE2 treatment period.

The following study periods are defined for the classification by study period:

- Screening Period: Prior to the date of first dose of study drug
- Initial Treatment Period is defined as the time from the first study drug administration up to the start of the Maintenance Treatment Period
- Maintenance Treatment Period starts with the first study drug administration at or after the Week 16 visit
- Open-Label Extension Period starts with the first study drug administration at or after the Week 48 visit
- SFU Period is 20 weeks after the final dose of IMP in the double-blind Treatment Period or Open-Label Extension Period
- Open-Label Extension 2 Period starts with the first study drug administration at or after the Week 144/OLE2 Baseline visit
- SFU2 Period is 20 weeks after the final dose of IMP in the OLE2.

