## **3.6 Treatment assignment and treatment groups**

It is expected that subjects receive treatment as randomized and hence safety analyses will be based on the SS, as randomized. However, if after unblinding it is determined that subjects randomized to a treatment arm had never received such treatment, then for safety analysis, these subjects will be reallocated to the appropriate received treatment groups, unless otherwise specified.

If subjects randomized to secukinumab received bimekizumab at any time, then for safety analyses these subjects will be reallocated to the appropriate bimekizumab treatment group, unless otherwise specified. Subjects randomized to bimekizumab will only be reallocated to the secukinumab treatment group if they never received bimekizumab.

Efficacy analyses should be performed according to randomized treatment and not actual treatment received.

Randomized treatment groups are Bimekizumab 320mg Q4W and Secukinumab 300mg Q4W. Maintenance treatment groups are Bimekizumab 320mg Q4W, Bimekizumab 320mg Q8W, and Secukinumab 300mg Q4W.

Re-randomized (Open-Label extension) treatment groups are Bimekizumab 320mg Q4W and Bimekizumab 320mg Q8W. Unless otherwise specified, the OLE period will be summarized by treatment sequence comprising randomized treatment at Baseline and OLE period treatment at Week 48.

The following treatment sequences will be used to summarize efficacy data and specific safety data related to laboratory, ECG, PHQ-9, eC-SSRS, and vital signs assessments:

- Subjects receiving bimekizumab in the double-blind treatment period:
  - Initiating OLE on bimekizumab Q8W

- 
- Initiating OLE on bimekizumab Q4W
  - Subjects receiving secukinumab in the double-blind treatment period
    - Initiating OLE on bimekizumab Q8W
    - Initiating OLE on bimekizumab Q4W
  - All Subjects

Adverse event data (including for a subgroup of subjects who switched from Q4W to Q8W during OLE period) and study compliance data will be summarized in 2 treatment groups based on the dose most recently received prior to the date of the event or assessment

- Bimekizumab 320mg Q8W
- Bimekizumab 320mg Q4W
- Bimekizumab Total

In addition, the following key efficacy variables:

- PASI90 response
- PASI100 response
- IGA Clear or Almost Clear (with at least a 2-category improvement from Baseline)
- IGA Clear (with at least a 2-category improvement from Baseline)

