#### Time at risk (days)

Total time at risk attributed to each dose will be obtained by summing the time(s) at risk at each specific dose in each individual study period and deducting n-1, where n is the number of non-consecutive periods covered that are being summed. Total time at risk attributed to BKZ Total will be obtained by using the time at risk algorithms specified for subjects who do not switch study treatments in Section 10.1.5.1.

- Time at risk at each specific dose in each individual study period is calculated separately as follows:

- Attributed to BKZ 320mg Q4W:

- Date of first BKZ 320mg Q8W dose in the next study period – date of first BKZ 320mg Q4W dose in the current study period.

Note: If BKZ 320mg Q4W is the last dosing schedule received in the last study period, then this calculation reverts to:

- For all subjects, use the minimum of the following:
- Date of last BKZ 320mg Q4W dose in the current study period – date of first BKZ 320mg Q4W dose in the current study period + 140 days.
- Date of first BKZ 320mg Q8W dose in OLE2 - date of first BKZ 320mg Q4W dose in the Open-Label Extension Period + 1 day. The OLE and The OLE2 treatment periods should not overlap by more than 1 day
- Date of last clinical contact – date of first BKZ 320mg Q4W dose in the OLE Period + 1.
- Date of death – date of first BKZ 320mg Q4W dose in the current study period + 1

- Attributed to BKZ 320mg Q8W:

- Date of first BKZ 320mg Q4W dose in the next study period – date of first BKZ 320mg Q8W dose in the current study period.

Note: If BKZ 320mg Q8W is the last dosing schedule received in the last study period, then this calculation reverts to:

- For subjects who die

Date of death – date of first BKZ 320mg Q8W dose in the current study period + 1.

For all other subjects, use the minimum of the following:

- Date of last BKZ 320mg Q8W dose in the current study period – date of first BKZ 320mg Q8W dose in the current study period + 140 days.
- Date of first dose in OLE2 - date of first BKZ 320mg Q8W dose in the Open-Label Extension Period + 1 day.
- Date of last clinical contact – date of first BKZ 320mg Q8W dose in the OLE Period + 1.

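### OLE time at risk on Q4W for subjects who switch to Q8W is counted from the last Q4W dose instead of the first, which shrinks the Q4W denominator in the OLS-based rate tables

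*SAP*

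**What the plan says.** Section 10.1.4.2 splits exposure for OLE switchers into a Q4W part, a Q8W part and a total. The Q4W time at risk is "Date of first BKZ 320mg Q8W dose in the OLE Period – date of last BKZ 320mg Q4W dose in the OLE Period" plus one day. The Amendment 4 change log prints the same line, so the wording is not an artefact of text extraction.

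The neighbouring rules start elsewhere:

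- **Q4W study medication duration, same section:** date of last Q4W dose minus "date of first BKZ 320mg Q4W dose in the OLE Period + 28 days".
- **Total BKZ time at risk, same section:** "Use the time at risk algorithm specified for subjects who do not switch study treatments in Section" 10.1.4.1, which runs from the first OLE dose.
- **Week 16 switch, section 10.1.3.2, Q4W time at risk:** "Date of first dose in the Maintenance Treatment Period - date of first dose + 1 day".
- **BKZ Set, section 10.1.5.2, Q4W time at risk:** first Q8W dose minus "date of first BKZ 320mg Q4W dose in the current study period".

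On the numerator side, section 3.6 assigns OLE adverse events to the dose most recently received, "including for a subgroup of subjects who switched from Q4W to Q8W during OLE period". Section 10.2 moves events to a new treatment only once that treatment has started. Section 10.2.1 makes the section 10.1 times at risk the basis of the exposure-adjusted summaries.

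**The concern.** The numerator and the denominator cover different stretches of time. Events on Q4W are collected from the first OLE Q4W dose until the switch. The denominator covers only the interval between the last Q4W dose and the first Q8W dose.

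The rule is also incoherent within the EAIR. Section 10.2.1 counts a subject with an event up to the first occurrence and a subject without one for the full time at risk. A Week 96 switcher whose first event falls on OLE day 100 would contribute 100 days, while an event-free subject with the same switch date would contribute 29.

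Section 10.1.4.2 says Q4W subjects should switch after Protocol Amendment 5.0, so the line governs most Q4W subjects who remain in the OLE. Q8W time is counted in full. The formula alone would therefore make Q4W look worse than Q8W in the OLE tables, including those for the safety topics of interest.

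**Working it through.** The SAP states no exposure, rate or factor for this line, so there is no figure of its own to reproduce. The check is date arithmetic on the planned schedule.

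**Inputs**

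- OLE start, section 2.3.2: "Open-Label Extension Period starts with the first study drug administration at or after the Week 48 visit". On schedule, the first OLE Q4W dose is at Week 48.
- Switch visits, Table 7-2 footnote a: "dosing interval will change from Q4W to Q8W at Week 64 or at the next scheduled clinic visit". The marked visits are Weeks 64, 72, 84, 96, 108, 120 and 132.
- Footnote b (Weeks 64, 72, 96, 120): a dose is given at the switch visit. Taken as the first Q8W dose, it comes 4 weeks after the last Q4W dose.
- Footnote c (Weeks 84, 108, 132): no dose is given at the visit. The first Q8W dose follows 4 weeks later, 8 weeks after the last Q4W dose.

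**Formulas**

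- As written: 7 × (week of first Q8W dose − week of last Q4W dose) + 1
- From the first dose: 7 × (week of first Q8W dose − 48) + 1

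| Switch visit | Last Q4W dose (week) | First Q8W dose (week) | As written (days) | From first dose (days) | Ratio |
|---|---|---|---|---|---|
| 64 | 60 | 64 | 29 | 113 | 3.9 |
| 72 | 68 | 72 | 29 | 169 | 5.8 |
| 84 | 80 | 88 | 57 | 281 | 4.9 |
| 96 | 92 | 96 | 29 | 337 | 11.6 |
| 108 | 104 | 112 | 57 | 449 | 7.9 |
| 120 | 116 | 120 | 29 | 505 | 17.4 |
| 132 | 128 | 136 | 57 | 617 | 10.8 |

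**EAER in switchers.** The EAER divides by total time at risk, so it is inflated by the ratio itself. An assumed true rate of 150 per 100 patient-years would print as 150 × 113/29 ≈ 584 for Week 64 switchers and 150 × 505/29 ≈ 2,612 for Week 120 switchers.

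**Other reading of footnote b.** If the dose at the switch visit is classed as the last Q4W dose, the first Q8W dose comes 8 weeks later and the as-written time is 57 days. The ratios become 169/57 = 3.0 (Week 64), 225/57 = 3.9 (Week 72), 393/57 = 6.9 (Week 96) and 561/57 = 9.8 (Week 120). The footnote c visits do not change.

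**EAIR in switchers.** Subjects with an event contribute time to first event under either rule. Assume a constant rate λ per year, true time T and as-written time S. Mean exposure is (1 − e^(−λT))/λ with the correct rule. As written it is lower by (T − S)e^(−λT). The ratio of the two gives the inflation:

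- λ = 0.01 (1 per 100 patient-years): 3.9 (Week 64) to 15.6 (Week 120)
- λ = 0.2 (20 per 100): 3.6 to 6.0 across the switch visits
- λ = 1 (100 per 100): 1.5 to 2.9 across the switch visits

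For example, at Week 64 with λ = 1, T = 0.309 and S = 0.079 years. The correct mean exposure is 0.266, the as-written mean is 0.266 − 0.230 × 0.734 = 0.097, and the ratio is 2.7.

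**Whole Q4W column.** Q4W subjects who never switch are counted in full under 10.1.4.1. If they hold a share f of the true Q4W person-time, a switcher ratio R becomes 1/(f + (1 − f)/R). With f = 0.10 (an assumption), 3.9 falls to 3.0 and 17.4 falls to 6.6.

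**Additivity.** For a subject who enters OLE2 at Week 144, Total BKZ time is 7 × (144 − 48) + 1 = 673 days.

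- Week 64 switch: Q8W time is 7 × 80 + 1 = 561. As written, 29 + 561 = 590. From the first dose, 113 + 561 − 1 = 673.
- Week 120 switch: Q8W time is 7 × 24 + 1 = 169. As written, 29 + 169 = 198. From the first dose, 505 + 169 − 1 = 673.

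**The case against.** The best defence is that this is a drafting slip whose intent is plain from the rules around it, and that no confirmatory conclusion rests on it. Both parts are fair. OLE Q4W versus Q8W is not a clean randomised contrast either, because Week 48 PASI90 non-responders are assigned to Q4W. None of this rescues the line, because a SAP formula is programmed as printed.

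Three narrower objections stand:

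- **Section 10.1.5.2 is not an exact parallel.** It runs to the first Q8W dose in the next study period and has no added day, whereas an OLE switch stays within one period. The case rests more firmly on the duration and Total rules of 10.1.4.2 itself and on 10.1.3.2.
- **The top of the range belongs to one visit and one convention.** The 17.4 needs a Week 120 switch and the first reading of footnote b. That reading fits the footnote better, but the SAP does not fix it. Section 9 groups OLE switches at Week 72 or 84 and at Week 96 or later, with no Week 64 group, so the 3.9 may also be untypical.
- **Column-level figures need inputs the SAP does not give,** namely how many subjects switch and when.

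A reader might infer that all OLE Q4W rates are 4 to 17 times too high. The SAP does not support that: the EAIR stops the clock at the first event, and non-switchers are counted in full. A reader might also infer that the secondary safety variables as a whole, and so the comparison with secukinumab, are compromised. They are not. Sections 10.1.1 to 10.1.3, the risk differences, Total BKZ and the BKZ Set rules do not use this line.

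**Conclusion.** The line is wrong as written and should be corrected before the Week 144 and final OLE tables are produced. In switchers who are dosed on schedule, Q4W time at risk is understated and the EAER overstated by about 3.9 to 17.4 times, with the dose at a footnote b visit taken as the first Q8W dose. Under the other convention, those visits give about 3.0 to 9.8. The EAIR factor is close to these values for rare events and falls as events become common; its figures rest on a constant-rate assumption. Column-level inflation is smaller by an amount the SAP does not let one compute.

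The damage is limited to the Q4W column of the OLS-based OLE exposure and adverse-event rate summaries. Within that column it is large enough to create an apparent Q4W excess over Q8W, and to put the OLS rates at odds with the BKZ Set rates.

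**What to change.** In the Q4W time-at-risk line of section 10.1.4.2, replace *last* with *first*. The time then runs from the first OLE Q4W dose to the first OLE Q8W dose, plus one day. The cost is one word, and a rerun of the OLS-based exposure and adverse-event rate tables if they were programmed from the printed line.

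A programming check that Q4W time plus Q8W time minus 1 equals the Total is worth adding, but only after two mismatches between 10.1.4.1 and 10.1.4.2 are reconciled. Otherwise it will raise false flags:

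- The death term in 10.1.4.1 lacks the added day that 10.1.4.2 has, so the parts exceed the Total by one day when death sets the limit.
- The OLE2 cap is the first OLE2 dose in 10.1.4.1 but the first OLE2 Q8W dose in 10.1.4.2. These dates differ for Group B subjects who restart on Q4W.

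The SAP should also state whether the dose at a footnote b switch visit counts as the last Q4W or the first Q8W dose, for exposure purposes only.
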